7.2.4 Visit 18: Post test

Visit will include the same assessments as visit 1

7.2.5 Visit 19: Post test 2 (short term retention)

Visits will include the same assessments as visit 1, 2 weeks following completion of training sessions

7.2.6 Visit 20: Post test 3 (long term retention)

Visits will include the same assessments as visit 1 six months following completion of training sessions

7.3 Duration of Participation

This study will require each participant to attend three 60-minute sessions per week for 5 weeks, as well as 5 separate test (pre and post) sessions, for a total of 20 sessions. If participant misses a session, it will be made up the following week, or by adding it to the end of training sessions. The first two separate pretests take place at visit 1 and 2, one to two weeks apart. The other additional testing sessions take place the visit after the conclusion of therapy sessions, 2 weeks later, and a 6 months following conclusion of therapy sessions.

8.0 Subject Numbers and Statistical Plan

8.1 Number of Subjects

We seek to recruit a total of 30 participants for the study per year between sites, and after screening and attrition rate, have 20 subjects a year complete the research procedures, for a total of 120 participants.

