7.2 Study Procedures

7.2.1 Visit 1 (pre-test 1):

Visit 1 (pre-test/screening): subjects will be consented, and then tested using standardized tests including the primary and secondary measures. In addition, the Edinburgh handedness inventory, Confidence in Arm and Hand Movement (CAHM), Multidimensional Scale of Perceived Social Support, NIH stroke scale, tests for comorbidities including testing of grip strength, visual neglect, and apraxia. If they meet criteria for the study, they will be randomly assigned to either the intervention or comparison condition. Tests may be videotaped for scoring and standardization purposes. Participant's names will not be associated with the videotapes. A data safety monitoring board will monitor the study for safety and to minimize risk.

7.2.2 Visit 2 (pre-test 2):

Visit 2 will include the same assessments as visit 1 to establish stability in baseline measures. Participants will also receive an MRI of the brain, which will take about one hour, as long as they are able to have one. The research grade MRI is used for data analysis regarding lesion location and volume. It is standard for studies of this nature to collect this information.

7.2.3 Visit 3-17:

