8.2 Sample size determination

Based on our primary outcome measures (Barthel, FIM-motor, Abilhand, UEFM, JTHFT) the proposed sample size of 60 participants per group provides adequate power (≥ 0.80) to assess each prediction when the effect size (Cohen's f) is 0.35 or greater. Cohen suggested that researchers consider $f=0.1$ as a small effect, $f=0.25$ as a medium effect, and $f=0.4$ as a large effect. To determine sample size, we used a power analysis program, SOLO [81], and computer simulation. SOLO permitted us to vary effect sizes and determine the test's power for a fixed group size. The simulation permitted us to use our pilot data to generate multivariate normal data; fit a model with fixed effects for group, test, and group by test interaction; conduct tests to include those for the linear contrasts; and record the p-value and associated effect size. The pilot data was particularly useful because the participants had been chosen so that they would span the expected impairment levels, and included right- and left-hemisphere-damaged participants. We will go through the major measures and analyses for each aim below. We have collected pilot data for 15 participants, using a cross-over design, for Aims 1 and 2, which provide preliminary support for our predictions.

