8.3 Statistical methods

To assess our intervention, we will fit linear mixed models (LMMs) with single-degree-of-freedom linear contrasts [80] to determine if the data support our predictions (see next section). We will use a linear mixed model with main effects for group (experimental, control) and time (Test) and the group by time interaction simply provides a more flexible approach to the typical analysis of variance (ANOVA) model for a randomized pretest-posttest design. Specifically, LMMs will permit us to account for participant matching with a random cluster effect; and they permit each participant to have her or his initial value (random intercept) and different change patterns across the tests (random coefficients for an underlying piecewise regression). LMMs allow us to use covariates to adjust for any potential confounders. Finally, these models can tolerate missing data on the response, which is not true of the standard ANOVA-based model.

Lesion Reconstruction Methods: [name]'s laboratory personnel will reconstruct stroke lesions from the research grade MRI scans. They will superimpose lesions on each axial slice to identify common areas of lesion overlap associated with damage to the right or left hemisphere and to assess comparability of intrahemispheric lesion location in our two tracks. This grant will not specifically examine intrahemispheric lesion location, but these data will provide pilot data for future studies. To calculate the CST lesion load, we will use the tractography based atlas of human brain connections from the natbrain lab [72]. We will use the MRICron descriptive tool for the calculation of the CST-lesion overlap volume. The binary lesion mask file will be overlaid onto either the left or right binary template CST atlas, and the percentage of CST which overlaps with the lesion is calculated.

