16.2 Feasibility of recruiting the required number of subjects

Previous experience indicates that we can recruit a minimum of 20 eligible participants each year, from each site. This, in combination with the current databases at each site, makes the recruitment goal of 30 participants per year (15 per site), over the four-year course of recruitment (120 total), realistic. The HMC database has every stroke patient that is a patient in the hospital, which is over 100 per month. However, we have selective criteria, therefore we aim to recruit less than 5% of them.

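### The 120 behind 60 per group is the number recruited over four years; the plan's own completion rate gives about 80, or 40 per group, and the power statement does not allow for the difference

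*Combined protocol and SAP*

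**What the plan says.** Three places in the combined protocol and SAP carry the number 120 or its half.

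- **Section 8.1** sets recruitment at 30 a year across both sites and then, after screening and attrition, plans to "have 20 subjects a year complete the research procedures, for a total of 120 participants". It gives no number of years and does not say at which stage 120 is counted.
- **Section 16.2** gives the duration and the stage, in describing as realistic the "recruitment goal of 30 participants per year (15 per site), over the four-year course of recruitment (120 total"). It also says that "we can recruit a minimum of 20 eligible participants each year, from each site".
- **Section 8.2** states that "the proposed sample size of 60 participants per group provides adequate power (≥ 0.80) to assess each prediction" when Cohen's f is at least 0.35. It lists five clinical outcomes as the basis and describes a simulation from pilot data that would "fit a model with fixed effects for group, test, and group by test interaction" and test linear contrasts. It gives no alpha and no loss rate.

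Three other provisions bear on the count. Section 7.2.1 places screening and consent at visit 1, and then: "If they meet criteria for the study, they will be randomly assigned to either the intervention or comparison condition". Section 3.3.2 uses a withdrawn subject's data if there is enough of it and otherwise replaces the subject. Section 8.3 says of the mixed models that "these models can tolerate missing data on the response".

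**The concern.** The same 120 serves two purposes that cannot both hold at the stated rates. In 16.2 it is the intake. In 8.2, as 60 per group, it is the number on which power is calculated. Section 8.1 sits between them, with a one-third loss from intake to completion and 120 still at the end of the sentence.

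Screening failures make this more than loose wording. Under 7.2.1 a person who fails the criteria at visit 1 is never randomised, so cannot belong to either group of 60. If any of the 30 recruited a year fail screening, as 8.1 implies, the groups start below 60 before any attrition.

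Two things are at stake. Anyone following accrual, including the DSMB that 18.4 asks to monitor it, cannot tell which count 120 is the target for. And the power statement is not shown to apply to the number of participants that the plan would produce.

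**Working it through.** **Counts**

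Inputs: 30 recruited and 20 completing per year (8.1); four years of recruitment (16.2); two equal groups (60 per group in 8.2).

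1. Reproducing the plan's figure: 30 × 4 = 120, and 120 / 2 = 60 per group. The figure is reproduced exactly, but only as a recruited number.
2. Completers over the same years: 20 × 4 = 80, and 80 / 2 = 40 per group. Completion is 80 / 120 = 67%.
3. Reading 120 as completers would need 120 / 20 = 6 years, or 120 / (20/30) = 180 recruited, which is 180 / 4 = 45 a year. Neither is planned.
4. Number randomised: 8.1 does not split the yearly loss of 10 between screening and attrition. If all of it is screening failure, 80 are randomised; if all of it is attrition, 120 are. The range before replacement is therefore 80 to 120.

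**Power**

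This is an approximate check with a two-group F test on 1 and 2n − 2 degrees of freedom and noncentrality λ = 2n × f², where n is the number per group. It is not the planned mixed-model contrast, which uses repeated tests and within-person correlation. At f = 0.35, f² = 0.1225.

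- n = 60: λ = 120 × 0.1225 = 14.7, with 118 denominator df.
- n = 40: λ = 80 × 0.1225 = 9.8, with 78 denominator df.

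Alpha is not in the documents, so a range is shown. The value 0.01 is 0.05 / 5, for the five outcomes listed in 8.2; 0.025 is an intermediate value.

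| Alpha (two-sided, assumed) | Power, 60 per group | Power, 40 per group |
|---|---|---|
| 0.05 | 0.967 | 0.871 |
| 0.025 | 0.940 | 0.799 |
| 0.01 | 0.886 | 0.687 |

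At 60 per group, the claim of at least 0.80 is met throughout this range. At 40 per group it is met at 0.05, is marginal at 0.025 and is missed at 0.01.

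**Scope of the power statement**

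The power claim in 8.2 covers every prediction. The method it describes covers group, test and group-by-test effects. Aim 2 in 1.1 predicts correlations between JTHFT improvement and kinematic variance within each hemisphere group, and no calculation for these is shown.

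**The case against.** The strongest reply is that completers are not the analysed number. A mixed model keeps a randomised participant who misses some tests, 3.3.2 replaces those who leave too little data, and 16.2 claims at least 20 eligible people per site per year, or 20 × 2 × 4 = 160 over four years. On that view 60 per group could be reached.

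Part of this stands. These provisions may narrow the gap, and 40 per group should be read as the lower end of the analysed number, not as a forecast. But none of them is counted in the 120. The recruitment goal stays at 30 a year whatever the capacity, replacement has no number attached, and tolerance of missing responses does not bring back people who were never randomised.

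A second reply is that the stated power claim survives, so only wording is at fault. That is right under an unadjusted two-sided 0.05 and wrong if alpha is shared over the five outcomes. The documents do not say which applies. The check also simplifies the planned analysis, so it cannot settle the matter either way.

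A third reply concerns Aim 2. The power sentence opens from the listed clinical outcomes, and 1.3 makes early and late positional variance secondary endpoints. A reader might infer that the plan claims power for the Aim 2 correlations and lacks it. The documents do not support that: the likelier reading is that Aim 2 lay outside the calculation. What remains is that 8.2 does not say so.

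**Conclusion.** The count is inconsistent as written. Section 16.2 makes 120 the number recruited, the rate in 8.1 gives 80 completers over those four years, and 8.2 uses 60 per group with no allowance for the losses that 8.1 names. This rests on the documents' own figures, with the duration taken from 16.2 because 8.1 gives none.

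The effect on power is conditional. At f = 0.35, going from 60 to 40 per group lowers approximate power from 0.97 to 0.87 at 0.05 and from 0.89 to 0.69 at 0.01. These figures assume the two-group F test, equal groups and the stated alphas.

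A reader might infer that the trial is underpowered, or that 60 per group is certain to be missed. The documents support neither. Alpha is unstated, the number randomised cannot be derived, and replacement and partial data could raise the analysed number. The supportable conclusion is that 60 per group is not shown to be reached at the stated rates, and that whether 0.80 holds at the lower end depends on an alpha the plan does not give. It should be corrected, but it is not evidence of a failed design.

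**What to change.** - **8.1, 8.2 and 16.2:** give the numbers recruited, randomised and completing separately, and say whether replacements count towards the total. Unless the rate or duration is changed, write 120 recruited and about 80 completing (about 40 per group). Split the loss from 30 to 20 a year into screening failure and attrition, so that the randomised number can be stated.
- **8.2:** state alpha and how it is applied across the outcomes. Rerun the existing simulation at the expected analysed number per group; the figures here are only a check on it. Limit the power claim to the predictions that were simulated, and say that Aim 2 is not among them unless a calculation is added.
- **Minor reporting points:** 8.3 promises contrasts "to determine if the data support our predictions (see next section"), but the section that follows is 9.0 on confidentiality. Correct the pointer or add the contrasts, including those for prediction 1a and Aim 3.

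The cost is wording in four sections (8.1, 8.2, 8.3 and 16.2) and one rerun of a simulation that already exists. No extra patients are needed. The downside is a less favourable stated sample size and power.

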8.2 Sample size determination

Based on our primary outcome measures (Barthel, FIM-motor, Abilhand, UEFM, JTHFT) the proposed sample size of 60 participants per group provides adequate power (≥ 0.80) to assess each prediction when the effect size (Cohen's f) is 0.35 or greater. Cohen suggested that researchers consider $f=0.1$ as a small effect, $f=0.25$ as a medium effect, and $f=0.4$ as a large effect. To determine sample size, we used a power analysis program, SOLO [81], and computer simulation. SOLO permitted us to vary effect sizes and determine the test's power for a fixed group size. The simulation permitted us to use our pilot data to generate multivariate normal data; fit a model with fixed effects for group, test, and group by test interaction; conduct tests to include those for the linear contrasts; and record the p-value and associated effect size. The pilot data was particularly useful because the participants had been chosen so that they would span the expected impairment levels, and included right- and left-hemisphere-damaged participants. We will go through the major measures and analyses for each aim below. We have collected pilot data for 15 participants, using a cross-over design, for Aims 1 and 2, which provide preliminary support for our predictions.

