Aim 1: To determine whether non-paretic arm VRMT in chronic stroke survivors with severe paresis will produce durable improvements in non-paretic arm motor performance that will generalize to improve functional activities and functional independence to a greater extent than conventional therapy focused on the paretic arm. We predict that: 1a) Unilateral VRMT training of the non-paretic arm will produce functional improvements in non-paretic arm motor performance (JTHFT), 1b) Conventional therapy focused on the paretic arm should decrease paretic arm impairment (Fugl-Meyer) to a greater or equal extent than non-paretic arm VRMT. We will assess paretic arm impairment level using the upper extremity component of the Fugl-Meyer Assessment (UEFM) as our primary measure, and "work area" using kinematic analysis, as detailed by Dewald and Co-workers [5] as our secondary measure. 1c) The effects of non-paretic arm VRMT will generalize to functional activities (Abilhand) and functional independence (FIM-motor/Barthel) to a greater extent than conventional paretic arm therapy. This aim provides a strong test of our hypothesis that non-paretic arm motor training will have a greater impact on functional independence than conventional paretic arm training in patients who lack paretic hand function, a prediction supported by our pilot data (see Figure 8).

Aim 2: To determine whether intervention-induced improvements in non-paretic arm performance are associated with improvements in hemisphere-specific reaching kinematics. We predict that VRMT-induced improvements in performance will be correlated with reductions in hemisphere-specific motor deficits [6-9], which are targeted by the VR component of our intervention. We will test this using a planar reaching paradigm that we developed and employed in the previous cycle of this grant for

quantifying hemisphere-specific non-paretic arm kinematics [6]. We predict that improvements in functional performance (JTHFT) will correlate better with *early trajectory variance* in LHD patients, but with *late trajectory variance* in RHD patients. These variables have previously been associated with left and right hemisphere processes, respectively.

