1.2 Primary Study Endpoints

Non-Paretic Arm Evaluation: Jebsen-Taylor Hand Function Test
Paretic Arm Evaluation: Upper-Extremity Fugl-Meyer Assessment
Upper Extremity Functional Activity: Abilhand Assessment
Functional Independence: Barthel Index

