1.3 Secondary Study Endpoints

Functional Independence Measure (FIM)-motor component

Kinematic Outcomes:

Positional Variance (Early and Late):

- Peak Velocity,
- End point of movement (tangential velocity minimum, after peak velocity that has an amplitude of less than 15% of maximum velocity)

Work Area (Paretic Arm)

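### The primary endpoint lists contradict each other: FIM-motor is secondary in Section 1.3 but primary in Section 8.2, so functional independence has two candidate primary scales and no rule for choosing between them

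*Combined protocol and SAP*

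**What the plan says.** Four places in the combined protocol and SAP bear on which outcomes are primary.

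- Section 1.2 lists four primary endpoints: JTHFT, UEFM, Abilhand and, for the last domain, "Functional Independence: Barthel Index".
- Section 1.3 opens its list of secondary endpoints with "Functional Independence Measure (FIM)-motor component".
- Section 8.2 begins the sample size argument with "Based on our primary outcome measures (Barthel, FIM-motor, Abilhand, UEFM, JTHFT", which is five measures. It states power of at least 0.80 for each prediction with 60 per group at Cohen's f of 0.35 or more.
- Section 1.1, prediction 1c, refers to "functional independence (FIM-motor/Barthel" and does not rank the two scales.

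On the claim itself, Aim 1 says that the benefit "will generalize to improve functional activities and functional independence to a greater extent than conventional therapy". Prediction 1a reads "Unilateral VRMT training of the non-paretic arm will produce functional improvements in non-paretic arm motor performance (JTHFT" and names no comparator. Prediction 1b runs the other way: the control therapy should reduce paretic arm impairment "to a greater or equal extent than non-paretic arm VRMT".

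On the analysis, Section 8.2 announces "We will go through the major measures and analyses for each aim below", and Section 8.3 refers the reader to a following section for the predictions. Section 8.3 does name the model (linear mixed, with group, time and their interaction) and the type of test (linear contrasts with one degree of freedom). What follows it is lesion reconstruction and then Section 9.0 on confidentiality. Section 7.3 sets three post-tests: after training, at 2 weeks and at 6 months.

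**The concern.** FIM-motor cannot be both secondary and primary. The disputed scale measures functional independence, the outcome by which Aim 1 proposes to show that training the non-paretic arm does more than conventional therapy. Nothing in these documents says which scale decides, at what significance level, at which visit or across which visits, or whether one primary result or all of them are needed.

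Unless that text exists elsewhere and was fixed in advance, those choices could be made after the results are known. If either scale may carry the claim, the false-positive rate rises above the nominal level. If all primaries must succeed, the error rate is safe, but the power in Section 8.2 is stated prediction by prediction and overstates the power of the joint claim. The plan has to say which rule applies.

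**Working it through.** **1. The lists side by side.**

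| Measure | 1.2 / 1.3 | 8.2 | Prediction |
|---|---|---|---|
| JTHFT | primary | primary | 1a |
| UEFM | primary | primary | 1b |
| Abilhand | primary | primary | 1c |
| Barthel | primary | primary | 1c |
| FIM-motor | secondary | primary | 1c, unranked beside Barthel |

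Four measures agree and one does not. All the lists are intact, and the numbering runs 8.2, 8.3, 9.0 without a gap, so lost text does not explain the conflict.

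**2. The plan's own power figure.** Inputs from Section 8.2: 60 per group, f = 0.35, power at least 0.80. Alpha is not stated; two-sided 0.05 is assumed here and below. For a two-sample t-test, d = 2f = 0.70, the noncentrality is 0.70 × √(60/2) = 3.834 on 118 degrees of freedom, and power is 0.967. That satisfies the statement but does not reproduce 0.80 as a value: this test already reaches 0.80 at f = 0.26. The planned mixed-model contrast cannot be reconstructed, so both ends are carried below: exactly 0.80 per test (the stated floor) and 0.967.

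**3. Either functional-independence scale may count.** With k tests at critical value c = 1.960 and common correlation ρ,

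P(at least one) = 1 − ∫ φ(u) [Φ((c − √ρ·u)/√(1−ρ)) − Φ((−c − √ρ·u)/√(1−ρ))]^k du.

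At ρ = 0 and k = 2 this is 1 − 0.95² = 9.75%. At ρ = 0.5 it is 9.07%, and at 0.9 it is 7.04%. Counting only errors in favour of VRMT, ρ = 0 gives 1 − 0.975² = 4.94%, then 4.54% and 3.52%, against 2.5%. Zero correlation is an extreme bound for two scales of one construct.

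**4. A hypothetical upper case.** Suppose that any one of JTHFT, Abilhand or Barthel were enough. This assumes that JTHFT is compared between groups and leaves UEFM out because 1b predicts the opposite direction. With k = 3: 1 − 0.95³ = 14.3% at ρ = 0, then 12.5% and 8.4%.

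**5. All three must succeed.** There is no inflation. Joint power is ∫ φ(u) Φ((δ + √ρ·u)/√(1−ρ))³ du, where δ is the normal quantile of the per-test power.

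| Per-test power | ρ = 0 | ρ = 0.5 | ρ = 0.9 |
|---|---|---|---|
| 0.80 (δ = 0.842) | 0.80³ = 0.51 | 0.61 | 0.72 |
| 0.967 | 0.967³ = 0.90 | 0.92 | 0.95 |

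**6. Fixed sequence at the 0.80 floor.** The third endpoint is reached if the first two succeed: 0.80² = 0.64 at ρ = 0, then 0.69 and 0.75. It is won with the probabilities in step 5, 0.51 to 0.72.

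**7. Splitting alpha over three (0.05/3).** The simple t-test has power 0.92 with 60 analysed per group. Sections 8.1 and 16.2 can be read as 20 completers a year for four years, which is 80, or 40 per group; power is then 0.75.

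None of these figures counts choice among the three post-tests.

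**The case against.** The strongest reply is that the plan says more than it is given credit for. Section 8.3 names single-degree-of-freedom contrasts in a mixed model with a group-by-time term, and Section 8.2 says that such contrasts were simulated. Aim 1 joins functional activities and functional independence, Section 1.2 gives each primary its own domain, and Section 8.2 powers each prediction separately. The detailed analyses may sit in the grant, which Section 18.4 mentions as uploaded.

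Much of this stands, and it rules out several stronger readings that a reader might infer.

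- That the plan has no contrast at all. It names the type; what is absent is the coefficients and time points.
- That any one significant primary counts as success. No passage offers this rule, so the 14.3% is a hypothetical upper case. Aim 1 is closer to requiring all, and inference prediction by prediction is a third reading.
- That a single deciding visit is required. Aim 1 asks for durable gains and the later post-tests are labelled as retention, so a prespecified contrast across post-tests would serve equally well.
- That the trial is too small. The 0.80 in Section 8.2 is a floor, and a simple t-test with 60 analysed per group has 0.967.
- That the analysis was never specified anywhere. The documents show only that it is not here.

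None of this removes the conflict over FIM-motor or supplies a success rule.

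**Conclusion.** The contradiction is exact and wrong as written: four primaries in Section 1.2, five in Section 8.2, with FIM-motor secondary in Section 1.3. Missing alpha and contrast wording would on its own be missing detail. It matters here because nothing else in the documents settles which scale decides functional independence.

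If either scale may count, the false-positive rate is 7.0% to 9.8% in place of 5%, or 3.5% to 4.9% in VRMT's favour in place of 2.5%. If JTHFT, Abilhand and Barthel must all succeed, the error rate is controlled and joint power lies between 0.51 and 0.95, depending on the correlation and on the true power of the planned contrast. These figures assume two-sided 0.05 per test, one test per endpoint and correlations of 0 to 0.9, none of which the plan states. They do not show that 60 per group is wrong.

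**What to change.** 1. Use one primary list in Sections 1.1 (prediction 1c), 1.2, 1.3 and 8.2, with a single primary for functional independence. Barthel as primary and FIM-motor as secondary would match 1.2 and 1.3. The choice is the sponsor's and must be made before outcome data are compared by group.
2. Replace the forward reference in Section 8.3 with the defined group-by-time contrast for each primary: either one visit, or a prespecified contrast across post-tests consistent with a durable effect. State whether JTHFT in prediction 1a is compared between groups. If the grant already contains this text, insert it.
3. State alpha and one rule for the endpoints on which VRMT is expected to be superior: all succeed at two-sided 0.05, a fixed sequence, or Holm at a familywise two-sided 0.05. State separately how UEFM is handled for prediction 1b and Aim 3.
4. Restate the Section 8.2 power under that rule, using the simulation already described there.

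The cost is wording, one rerun of an existing simulation, and some power. Requiring all three gives the joint power in step 5 of the working. A fixed sequence splits no alpha, but at the 0.80 floor the third endpoint is reached with probability 0.64 to 0.75 and won with 0.51 to 0.72. For Holm, the strictest step is 0.05/3, where a simple t-test has 0.92 with 60 analysed per group, or 0.75 with 40. No increase in enrolment is proposed.
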